5. SAMPLE SIZE AND POWER/PRECISION CALCULATIONS

5.1. Sample Size Calculations

As the primary objective of the study is to obtain an estimate of physician adherence to the fondaparinux prescribing information for SVT, overall and per country, a methodology that takes into consideration the study design, i.e. patients nested within each physician and within each site, has been identified. This explicitly recognises the fact that the prescribing for different patients consulting the same physician is unlikely to be independent and will be correlated (the amount of correlation represented by the intra-class correlation coefficient). It is assumed that prescribing for patients consulting different physicians and sites is independent.

For any given total patient sample size, the higher the ratio of the number of participant physicians to the number of patients each physician recruits, the greater the power achieved. The design of the study intends to allow sites some flexibility (in order to ensure site participation) in the number of physicians and number of patients each may recruit. This flexibility is described in Table 2 below with minimum and target numbers defined. Upper limits in terms of the maximum permissible number of patients per physician and the maximum permissible number of physicians per site are also stated.

Table 2: Enrolment - Minimum, Target and Upper Limits Defined

		Enrolment	
	Target	Minimum	Upper limit
Physicians per country	30*	19	30*
Patients per physician	7	7	10
Patients per country	210*	133	210*
Physicians per site	2	1	5
Patients per site	14	7	20
Sites per country	15*	10	15*
Countries	4	4	4
Total No. Patients	840	532	840

^{*} Average across all countries

The patient sample calculations were based on using the technique described by Emrich and Piedmonte [6] contained within the R statistical package "mvtBinaryEP" [7]. Correlated binary data for a specific user-entered intraclass correlation coefficient could be generated.

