Monte Carlo simulations generating such correlated binary data (of the specified intra-class correlation, of the specified sample size, N, and assuming an underlying population probability of adherence of 0.8) were performed. For each simulated data set a Generalised Estimating Equation, GEE, containing a constant term was applied and the 95% confidence interval around the computed average percent adherence prediction was calculated. An indicator variable was created for each simulated data set which took the value 1 if the lower 95% confidence interval just described was above 60% and took the value 0 otherwise. The mean value of this indicator variable was then calculated across all simulation runs and represents the power of achieving a lower bound greater than 60% (given an assumed adherence rate of 80% and a specified intra-class correlation) from the stated sample size/mix.

Table 3 below demonstrates how the power can vary for the same patient sample size of 210 by varying the intra-class correlation and/or the mix of number of physicians and patients managed per physician. The higher the intra-class coefficient the greater the benefit from increasing the number of physicians selected and decreasing the number of patients managed per physician to generate the same total patient base. With this in mind it has also been decided that no one physician should provide more than ten patients to the study (see appendix 9.4).

Table 3: Power Calculations for Minimum and Target Physician Numbers with varying intra-class correlations

	Intra-class correlation	Power
Scenario 1 (210 patients)	0.1	0.998
30 physicians, 7 patients each	0.2	0.974
total 210 patients	0.25	0.963
	0.3	0.937
Scenario 2 (210 patients)	0.1	0.994
21 physicians, 10 patients each	0.2	0.950
total 210 patients	0.25	0.916
	0.3	0.874
Scenario 3 (180 patients)	0.1	0.981
18 physicians, 10 patients each	0.2	0.900
total 180 patients	0.25	0.854
	0.3	0.807
Scenario 4 (Minimum sample)	0.1	0.964
19 physicians, 7 patients each	0.2	0.891

0.804

total 133 patients	0.25	0.846

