5.2.1. Primary Analyses

Adherence estimates with confidence intervals will be derived using generalised estimating equations (GEE) overall and for each country [8]. The GEE will explicitly take into account the nesting of patients, per physician, within a medical practice.

Adherence in the current study will be defined as performing CUS, or other diagnostic imaging procedure, in order to rule out concomitant DVT prior to patients commencing fondaparinux therapy and ensuring that the recommended dose of fondaparinux is prescribed.

A sensitivity analysis will be conducted incorporating the length of the thrombus and the distance of the thrombus from the sapheno-femoral junction into the primary endpoint if the data is available.

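### The overall adherence GEE has no country stratum or weights; if the four countries differ, its interval is conservative and its value moves with the recruitment mix

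*Supplement*

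**What the plan says.** Section 5.2.1 (Primary Analyses): "Adherence estimates with confidence intervals will be derived using generalised estimating equations (GEE) overall and for each country". The next sentence sets out the structure: "The GEE will explicitly take into account the nesting of patients, per physician, within a medical practice". Country does not appear there, and no section gives a country term, stratum or weight for the overall figure. Section 4.3 makes the overall proportion part of the primary outcome, alongside the country results.

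The design is by country. Section 3.2 has one master list of sites per country. Section 4.1 selects sites at random from lists stratified by region within each country. Section 4.2 takes 12 to 18 sites per country into the main study, in proportion to population. In Table 2 (section 5.1) the targets of 30 physicians, 210 patients and 15 sites per country are averages across countries; the minimum is 19 physicians and 133 patients.

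The power simulation in section 5.1 is run "assuming an underlying population probability of adherence of 0.8", and in it "a Generalised Estimating Equation, GEE, containing a constant term was applied". Success means that "the lower 95% confidence interval just described was above 60" per cent. Section 5.1 also states: "It is assumed that prescribing for patients consulting different physicians and sites is independent".

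**The concern.** The four countries are fixed strata: sites are drawn within them, and the countries themselves are not sampled. In a pooled GEE without country, each cluster's residual is taken from the pooled mean. A fixed gap between countries therefore enters the robust variance as though it were chance variation between physicians or practices. The interval is then wider than the sampling design implies for these four countries.

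Without stated weights, each country also counts in proportion to the patients it supplies. The same four country rates can then give different overall figures, and the reader is not told which mix of countries the figure describes. Section 5.1 says the objective is to obtain an estimate, so its precision and meaning matter apart from any bound.

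**Working it through.** **Inputs from section 5.1:** 7 patients per physician; intra-class correlation (ICC, ρ) 0.1 to 0.3; mean adherence 0.80; target "30 physicians, 7 patients each" and minimum "19 physicians, 7 patients each" per country. **Assumed, not in the documents:** country rates 0.70/0.77/0.83/0.90 (70-90%) or 0.65/0.75/0.85/0.95 (65-95%), both averaging 0.80.

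**1. The plan's own figures.** Table 3 was re-simulated with 40,000 runs per cell: exchangeable correlated binary data, an intercept-only logit GEE clustered on physician, and a robust variance multiplied by k/(k-1) for k physicians. All 16 cells agree within 2 points. For example, at ICC 0.3: 0.955 against 0.937 (30 × 7), 0.874 against 0.874 (21 × 10), 0.811 against 0.807 (18 × 10) and 0.809 against 0.804 (19 × 7).

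**2. Interval, physicians as clusters.** Let w = mean of p(1-p) over countries × (1 + 6ρ)/7, b = mean of (p - 0.80)², and M = total physicians, split equally between countries.

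- Pooled SE² = (w + b)/M; stratified SE² = w/M; width ratio = √(1 + b/w).
- 70-90%, ρ = 0.2: w = 0.15455 × 2.2/7 = 0.04857; b = 0.00545; ratio = √1.112 = 1.055.
- 65-95%, ρ = 0.2: w = 0.1475 × 2.2/7 = 0.04636; b = 0.0125; ratio = √1.270 = 1.127.

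95% half-widths in percentage points, pooled / stratified:

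| Spread | ICC | 4 × 30 physicians | 4 × 19 physicians | Ratio |
|---|---|---|---|---|
| 70-90% | 0.1 | 3.61 / 3.36 | 4.54 / 4.23 | 1.074 |
| 70-90% | 0.2 | 4.16 / 3.94 | 5.23 / 4.96 | 1.055 |
| 70-90% | 0.3 | 4.64 / 4.45 | 5.83 / 5.59 | 1.043 |
| 65-95% | 0.1 | 3.85 / 3.29 | 4.83 / 4.13 | 1.171 |
| 65-95% | 0.2 | 4.34 / 3.85 | 5.45 / 4.84 | 1.127 |
| 65-95% | 0.3 | 4.78 / 4.35 | 6.01 / 5.46 | 1.101 |

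The excess is 4-17%, or about 0.2 to 0.7 points. With b = 0 the ratio is 1.

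**3. Interval, practices as clusters.** With two physicians per practice (the Table 2 target), independent as section 5.1 assumes, the within-country variance of a cluster mean halves while b stays. The ratio becomes √(1 + 2b/w): 1.08 to 1.14 for 70-90% and 1.19 to 1.32 for 65-95%, so 8-32% wider.

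**4. Value of the overall figure.** The expected pooled figure is Σ(physicians × rate)/Σ physicians, against 80.0% with equal weights.

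- 30/30/19/19 physicians, 70-90%: (21 + 23.1 + 15.77 + 17.1)/98 = 78.5%; in reverse order, 81.5%.
- 30/30/19/19, 65-95%: (19.5 + 22.5 + 16.15 + 18.05)/98 = 77.8%; in reverse order, 82.2%.
- 36/32/28/24 (12 to 18 sites × 2 physicians): 78.9% or 81.1% for 70-90%; 78.3% or 81.7% for 65-95%.

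The shift is 1.1 to 2.2 points either way.

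**5. The 60% bound.** The lowest value in step 4 is 77.8%. Subtracting the widest pooled half-width in the table (6.01) leaves about 72%. With practices as clusters at ICC 0.3 the half-width is 5.46 × 1.193 = 6.5, leaving about 71%. Simulated overall power is about 1.00 for 532 or 840 patients.

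**6. Small-sample check on the remedy.** 8,000 beta-binomial runs, ICC 0.2, 19 physicians per country, uncorrected SEs:

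- 70-90%: true SD 0.0254; pooled SE 0.0264 (+4%); stratified SE 0.0245 (-4%).
- 65-95%: true SD 0.0247; pooled SE 0.0276 (+12%); stratified SE 0.0239 (-3%).

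Multiplying the stratified SE by √(19/18) = 1.027 gives 0.0252 and 0.0246, within 1% of the true SD.

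**The case against.** No separate analysis plan is shown, and terms and weights for a pooled model are often settled there. Section 5.2.1 describes the nesting and lists no mean-model terms, so it is silent on country and does not rule it out. That stands as a caution. But the section does spell out what the GEE takes into account and stops at practice, and stratifying is a definite improvement that uses data already collected.

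A reader might infer from section 5.1 that the overall analysis is fixed as a constant-only model. The documents do not support this: the simulated samples are single-country ones of 133 to 210 patients, where no country term could exist. The independence assumption in section 5.1 is no evidence of a fault either, since it also holds within a country-stratified model.

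A reader might also infer that the weights are left wholly to recruitment. Section 4.2 makes site numbers proportionate to population, which gives rough weighting by design. It does not fix the weights, because Table 2 allows 1 to 5 physicians per site and 7 to 10 patients per physician. The shifts in step 4 also need recruitment to line up with adherence.

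The effect is small and conservative, and the planned country results would reveal any differences. All of that is accepted.

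Finally, too wide holds only for inference to these four countries. If the figure were read for the EU, treating countries as a random sample would give half-widths of about 9 to 14 points under the same two spreads (normal approximation). Both the pooled and the stratified interval would then be too narrow. This is a reason to state the target, not to leave country out.

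**Conclusion.** The point holds as a minor improvement. As described, the overall GEE has no country stratum or weight. For these four countries its interval would be about 4-17% wider than a stratified one with physicians as clusters, and 8-32% wider with two-physician practices as clusters. The expected overall figure would move by about 1 to 2 points with the recruitment mix. These sizes rest on assumed country rates of 70-90% and 65-95%, ICC 0.1 to 0.3 and 7 patients per physician; with equal country rates both effects vanish.

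It would be wrong to conclude that the overall result is unreliable or that the 60% lower bound is in doubt. The interval errs on the wide side, and overall power is about 1.00 either way.

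**What to change.** In section 5.2.1, obtain the overall estimate by stratifying the GEE by country, or by combining the country-specific GEE estimates as Σ a_c p_c with variance Σ a_c² V_c. State the weights a_c before analysis. The planned site shares are one option, since section 4.2 already ties them to population; the documents give no numerical shares, so the sponsor must write them down.

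Compute each V_c as a cluster-robust variance within country, multiplied by k_c/(k_c - 1), where k_c is the number of clusters in that country. The plan names no such correction, and the uncorrected stratified SE runs about 3-4% low at 19 physicians per country. Add that the overall interval refers to the four participating countries and not to the EU as a whole.

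The cost is a few sentences and a few lines of code, with no new data. The weights must be fixed in advance, and the overall figure may differ slightly from the crude pooled percentage. If countries do not differ, essentially nothing is lost.

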5.2.2. Secondary Analyses

Further analyses will investigate the four secondary endpoints, namely performing CUS or other diagnostic imaging procedure, prescribing of the recommended dose and the length of thrombus and the distance of the thrombus from the sapheno-femoral junction. The same methodology as applied to the primary analyses will be utilised here. Adherence estimates will be calculated overall and per country.

6. STUDY LIMITATIONS

The study objective focuses on evaluating physician adherence to fondaparinux prescribing information; that ultrasound is conducted prior to prescribing fondaparinux, and that the correct dose is administered.

The study involves the retrospective review of patient charts and it is acknowledged that certain additional information may not be available for all patients included in the study, for example:

- the rationale for prescribing a dose other than 2.5mg may not always have been recorded
- the planned and/or actual treatment duration may not be known
- patient non-adherence will not be known.

Note, as it is not the objective of this study to evaluate treatment outcomes, patient follow up will not be conducted as part of the study.

7. STUDY MANAGEMENT

7.1. Ethical Approval and subject confidentiality

ARW will work with the appropriate ethics committees and regulatory bodies to gain approval for the study in each of the planned countries.

7.2. Subject Confidentiality

CRFs will be stored and information entered into a secure database within the UK. All data will be collected, handled and processed in accordance with the UK Data Protection Act (1998). Each study site will be assigned a unique code and, likewise, each patient record collected will also be uniquely coded. No data that could identify the patient (for example, name and date of birth) will be collected and all data will be kept completely confidential. Aggregated data will be uploaded onto a secure (password-protected) database, where it will be held for the duration of the study. The database will then be passed to the Sponsor who will keep the data in accordance with legal and company data retention laws, as well as company specific data protection laws.

All information collected will be securely archived and kept for a maximum of 3 years after study completion.

7.3. Reporting of Adverse Drug Events

The present study does not require collection of any patient outcome or adverse event data following fondaparinux prescription. However any serious adverse events explicitly attributed to GSK products which are identified should be reported to the GSK's Central Safety Department within 24 hours of identification. Site investigators will be trained on GSK's reporting procedure, should the need arise during the study.

7.4. Study Milestones

EMA/CHMP Approval	October 2011
GSK Approval	April 2012
Site Identification & Assessment	April 2011 – December 2012
Feasibility Study & Review*	August 2012 – March 2013 Dependent upon launch date in each study country

Site Recruitment & EC Submissions*:

First Patient Included*:

September 2012 – June 2013
Dependent upon outcome of feasibility review and launch date in each study country

January 2013 – July 2013 (Country dependent)

Last Patient Included*: February 2013 – August 2013 (Country dependent)

Country Analyses Completion*: March 2013 – September 2013

Global Analyses and Report Completion*:

December 2013

7.5. Study Advisory Committee

Role

It is envisaged that the Study Advisory Committee will be comprised of a study representative (primary investigator) from each country and, if needed, a noninvestigator expert. The role of the committee will include:

- Leading regulatory/ ethical procedures in each country (i.e. ECs, informed consent, etc.)
- Advising on physician selection and recruitment in each country (if required)
- Contributing to the development of any associated publications once the study is complete.

7.6. Study Reporting and Publications

All data, results and intellectual property rights in the data and results derived from the study will be the property of the Sponsor (GSK), who may utilise the data in various ways, such as for submission to government regulatory authorities or disclosure to other investigators.

The Sponsor's policy is to seek publication of all study results including this

^{*}still pending

proposed study. Each investigator, whilst free to utilise data derived from the study for scientific purposes, will be asked to discuss any publication with the Sponsor prior to release and obtain written consent of the Sponsor on the intended publication. The Sponsor recognises the right of the investigator to publish the results upon completion of the study. However, the investigator will be asked to send a draft manuscript of the publication or abstract to the Sponsor thirty days in advance of submission in order to obtain approval prior to submission of the final version for publication. This will be reviewed promptly and approval will not be withheld unreasonably. In case of a difference of opinion between the Sponsor and the investigator(s), the contents of the publication will be discussed in order to find a solution which satisfies both parties.

7.7. Resourcing Needs

ARW (external to WWEpi) will be managing the study on behalf of GSK, including study set-up, physician recruitment, facilitating EC and regulatory submissions, contracting and data collection. Analyses and reporting will also be conducted by ARW.

9. APPENDICES

9.1 Fondaparinux prescribing information

PRESCRIBING INFORMATION FOR USE IN PATIENTS WITH SVT

Treatment of superficial-vein thrombosis

The recommended dose of fondaparinux is 2.5 mg once daily, administered by subcutaneous injection. Patients eligible for fondaparinux 2.5 mg treatment should have acute, symptomatic, isolated, spontaneous superficial-vein thrombosis of the lower limbs, at least 5 cm long and documented by ultrasonographic investigation or other objective methods. Treatment should be initiated as soon as possible following diagnosis and after exclusion of concomitant DVT or superficial-vein thrombosis within 3 cm from the saphenofemoral junction. Treatment should be continued for a minimum of 30 days and up to a maximum of 45 days in patients at high risk of thromboembolic complications. Patients could be recommended to self-inject the product when they are judged willing and able to do so. Physicians should provide clear instructions for self-injection.

Special populations

Renal impairment

Treatment of superficial-vein thrombosis - Fondaparinux should not be used in patients with creatinine clearance <20 ml/min. The dose should be reduced to 1.5 mg once daily in patients with creatinine clearance in the range of 20 to 50 ml/min. No dosage reduction is required for patients with mild renal impairment (creatinine clearance >50 ml/min). The safety and efficacy of 1.5 mg has not been studied.

Hepatic impairment

 Treatment of superficial-vein thrombosis - The safety and efficacy of fondaparinux in patients with severe hepatic impairment has not been studied, therefore fondaparinux is not recommended for use in these patients.

Low body weight

 Treatment of superficial-vein thrombosis - The safety and efficacy of fondaparinux in patients with body weight less than 50 kg has not been studied, therefore fondaparinux is not recommended for use in these patients.

9.1 Site Assessment Survey

SVT - Physician Prescribing Study Site assessment survey

Good morning/afternoon, I am calling from, a market research organisation specialising in healthcare.						
treat grate	ment of patients with Superfici	it centres for a study relating to the al Vein Thrombosis (SVT) and I would be questions to establish whether your in the study.				
Woul	d you be willing to answer these	e preliminary questions?				
☐ Ye	es 🔲 No					
If 'No	o', thank and close - record as a	'refused contact'.				
	, thank and close record as a	refused contact.				
1a.	Where do you mainly	☐ Hospital				
iu.	practice?	□ Office				
		☐ GP clinic/surgery				
		□ Other ()				
1b.	If 'hospital', how would you	☐ Teaching/University hospital				
	describe the type of	☐ Regional general hospital				
	hospital?	☐ Local general hospital				
		□ Other ()				
1c. And if 'hospital', what is the						
	name of the Department you work in?					
2.	Does your clinical setting	□ Yes				
	have routine access to					
	diagnostic imaging facilities					
3.	What is your primary	☐ Angiologist				
	specialty?	□ Radiologist				
		☐ Angio-surgeon				
		□ Vascular surgeon				
		☐ General surgeon				
		□ Internal medicine physician				
		☐ Phlebologist				

		□ General practitioner□ Emergency Room physician
		□ Other ()
4a.	Do you personally diagnose and treat patients with SVT and/or DVT?	□ Yes □ No
4b.	If 'no', would they be treated by someone else in your clinical setting or by someone else in a different clinical setting?	□ Same setting (specify who:) □ Different setting (specify which setting:) THANK AND CLOSE
		THAIN AND GEOSE
5a.	Including yourself, how many physicians in your setting will diagnose and treat patients with SVT?	
5b.	How many patients are currently being managed in your setting who have isolated SVT and how many have SVT with concomitant DVT?	isolated SVT SVT with concomitant DVT
6.	What proportion of these patients is treated with	% isolated SVT
7.	In a typical month, how many patients would your department diagnose with: a. Isolated SVT b. SVT with concomitant DVT	% SVT with concomitant DVT isolated SVT SVT with concomitant DVT
8a.	In what proportion of patients would you use the following procedures to diagnose SVT:	% physical examination% laboratory tests
	a. Physical examinationb. Laboratory testsc. Imaging procedures	% imaging procedures
8b.	In those patients for whom imaging is performed, would the details and results of diagnostic imaging be	□ Yes, imaging details□ Yes, imaging results□ No

9.	Following diagnosis, after what period of time would you normally follow up with an SVT patient?	 □ days	or	□ weeks
	routinely recorded in the patient's record?			

Thank you! Would you be interested in taking part in an observational, non-interventional study looking at the treatment of patients with SVT? The study will require each participating site to provide simple information on up to 14 patients meeting certain criteria from a representative sample of physicians within your practice setting.

If you are interested in the study, we will contact you again shortly with further information.

If 'Yes', please record full contact de	tails:
Name:	
Institution:	
Address:	Address:
	
	Telephone:
	
City:	Facsimilie:
_	_

If 'No': Can I please ask why you do not want to participate?

[INTERVIEWER: ALL ANSWERS SHOULD BE SPONTANEOUS. DO NOT READ OUT LIST BELOW]

TOO BUSY STUDY DOES NOT INTEREST DOCTOR ETHICAL CONCERNS ETHICAL RESTRICTIONS FROM PRACTICE/HOSPITAL DOES NOT WANT TO INVOLVE OWN PATIENTS	1 2 3 4 5	
OTHER [RESPONSE TO Q3b - REFERRED TO ANOTHER SETTING	7 6]	THANK AND CLOSE

